ALT or AST ≥ 10×ULN, and Total and direct bili < 1.5×ULN, and INR < 1.3 ×ULN	Interrupt dosing Monitor liver panel weekly If ALT/AST fall to <5×ULN, restart dosing; if ALT/AST fall to <1.5×, stop weekly monitoring	If the event does not resolve in 4 weeks or recurs, consult medical monitor about discontinuing study medication
ALT or AST \geq 5×ULN, and Total or direct bili \geq 1.5×ULN, or INR \geq 1.3 ×ULN		Discontinue study medication
ALT or AST $< 5 \times ULN$, and Total or direct bili $\ge 1.5 \times ULN$, or INR $\ge 1.3 \times ULN$	Interrupt dosing Monitor liver panel weekly If total and direct bili fall to <1.5 ×ULN and/or INR falls to < 1.3× on 2 consecutive tests, stop weekly monitoring and restart dosing	If the event does not resolve in 4 weeks or recurs, consult medical monitor about discontinuing study medication

For patients with Gilbert Syndrome, the 1.5 × ULN criteria for total and direct bilirubin will be replaced with a 1.5 × ULN for direct bilirubin and there will be no monitoring criteria for total bilirubin [Fontana 2020]. Other etiologies of ALT, AST, total and direct bilirubin, and INR elevations, such liver injury induced by other drugs and other viral infections, should be ruled out and treated accordingly.

If a patient prematurely discontinues study medication on or before Day 169, the Day 169/Early termination procedures will be performed. Patients who prematurely discontinue study medication will remain in the study for follow-on study assessments.

Patients will be followed for 52 weeks after the last dose of study medication (504 days beyond Day 1 for patients who complete the 24-week Treatment Period). AEs and concomitant medications will be recorded from the signing of informed consent to Day 169, but only MAEs, NCIs, and IMCs, which will be categorized as AEs, will be followed subsequently. Likewise, concomitant medications will be recorded through Day 169, but only immunosuppressive medications, vaccines, and new HBV treatments or medications associated with MAEs, NCIs, SAEs, hepatitis flares, or hepatic injury will be recorded beyond this point. At the end of the clinical trial, the decision about follow-on treatments and medical care will be made by the patient's medical physician or medical team in accordance with the usual standard of care.

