4.3. Rationale for Study Design

The study design replicates the general design of the prior Phase 1 study but extends treatment from 3 to 6 doses and the follow-up after the last dose of study medication from 30 to 52 weeks. These modifications will enhance the effects of study medication and provide a more extended follow-up to assess the durability of immunogenicity and AEs. Diaries will be collected for reactogenicity events at visits on Days 8 and 36, which correspond to 7±2 days after the first and second dose of study medication. A visit consisting of a targeted physical examination will be conducted 7±2 days after administration of Doses 1 and 2 of study medication. Safety laboratory testing (Table 3), including liver panel, for Doses 1 and 2 will be obtained during the visits conducted 7±2 after these doses of study medication. Safety laboratory for Doses 3, 4 and 5 will be obtained in the pre-treatment interval from 7 days after dose administration through the time that the next dose of study medication is administered. Safety labs after Dose 6 will be assessed at the Day 169 visit. Investigators will review the eligibility of all patients prior to dosing to determine if the next treatment is to be administered. Eligibility for the next treatment will include: 1) confirmation that patients did not meet a Stopping Rule (Section 7.1.1); 2) confirmation that the pre-treatment liver parameters are within acceptable ranges for treatment (Section 4.1); 3) confirmation that patients do not have a new confirmed or suspected IMC (Appendix 2). If abnormalities of ALT, AST, total bilirubin, direct bilirubin, or INR are reported after dosing is commenced, the monitoring and dosing rules of Section 4.1 will be applied. These procedures are considered sufficient to evaluate reactogenicity events, particularly after Doses 1 and 2, and guard

against hepatitis flares and liver function abnormalities that would preclude the scheduled administration of the next dose of study medication.

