- 1 If an authorized COVID-19 vaccine has been administered in proximity to a scheduled IP administration, a ± 3 day window is allowed for IP dosing.
- ^m After Day 169 or ET, only MAEs, NCIs and IMCs will be recorded.
- ⁿ A single blood sample will be collected for biobanking at the beginning of the study (prior to dosing on Day 1) and end of the study. This sample will be used for future analyses not specified in the protocol. Analysis will be limited to HBV serologic and HBV-specific DNA and RNA and patients' DNA will not be analyzed.
- ° Safety laboratory testing, including liver panel, for Doses 1 and 2 will be obtained during the visits conducted 7±2 days after these doses of study medication. Safety laboratory testing following Doses 3, 4 and 5 will be obtained in the interval from 7 days after dose administration and before the next dose of study medication is administered. Safety labs after Dose 6 will be assessed at the Day 169 visit.
- ^p Diaries will also be reviewed at the Day 85, Day 113, Day 141 and Day 169 visits

Table 2 Schedule of Events – Follow-up Period

	Follow-Up Period					
Study Visit	Day 232	Day 323	Day 414	Day 505 or ET ^a		
Completion of Week (number)	33	46	59	72		
Window (days)	±10 days	±10 days	±10 days	±10 days		
Visit may be conducted at home or work or in part as a telemedicine visit ^b	X		X			
Immunosuppressive medications, vaccines, and new HBV treatments (only) ^c	X	X	X	X		
Targeted and symptom-driven PE	X	X	X	X		
Height and weight				X		
Vital signs ^d	X	X	X	X		
ECG ^d				X		
Hematology and serum chemistry	X	X	X	X		
Liver panel	X	X	X	X		
HBV serology and viral markers ^e		X		X		
Whole blood for PBMC isolation		X		X		
MAEs, NCIs and IMCs (only) ^f	X	X	X	X		

AE = adverse event; ECG = electrocardiogram; ET = early termination; HBV = hepatitis B virus; HIV = human immunodeficiency virus; MAE = medically-attended adverse event; NCI = new-onset chronic illness; IMC = immune-mediated medical condition; PBMC = peripheral blood nonnuclear cell; PE = physical examination.

^a If a patient prematurely discontinues study medication before Day 505, Day 505/Early termination procedures will be performed.

^b A telemedicine visit would include a home visit by appropriate trained personnel to perform a target and symptom-driven physical and obtain vital signs and safety laboratories. The remaining portions of the visit may be conducted virtually by the study investigator.

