5.2. Inclusion Criteria

Patients who meet all of the following inclusion criteria may be included in the study.

- 1. Able and willing to provide informed consent
- 2. Men and women 18 to 65 years of age, inclusive
- 3. Body Mass Index (BMI) 18.0 to 34.9 kg/m², inclusive
- 4. Inactive, treatment-naïve CHB with documented HBsAg positivity for at least 12 months before Day 1. (The history of HBsAg positivity may be reduced to 6 months provided HBV anti-core IgM antibodies are negative).
- 5. qHBsAg ≥ 10 IU/mL but ≤ 200 IU/mL in the 12 months prior to Screening or from informed consent to randomization
 - If a patient has more than one qHBsAg value within 12 months and prior to randomization, the patient will be deemed eligible if any one measurement is within the eligible range.
- 6. AST, ALT, INR, albumin, total bilirubin (excluding patients with Gilbert Syndrome, who will only be eligible for study participation if total bilirubin is ≤ 3.0 mg/dL) and direct bilirubin within normal limits at screening. Note: ALT and AST elevations up to 1.5 x ULN are allowed if evidence of hepatic steatosis, defined as one of the following criteria: 1) fatty liver on ultrasound, or other imaging modality or Fibroscan controlled attenuation parameter (CAP) ≥ 260 dB/m. To qualify under these conditions, HBV DNA must be <2,000 IU/mL, and there must be no history or signs of liver disease other than fatty liver and HBV.
- 7. Negative drug screen at Screening unless prescribed by a medical practitioner for medical use (NB, recreational and prescription cannabis is allowed)
- 8. For women of childbearing potential (women who are not permanently sterile [documented hysterectomy, bilateral tubal ligation, salpingectomy, or oophorectomy] or postmenopausal [12 months with no menses without an alternative medical cause]):
 - a. Negative pregnancy test on Day 1
 - b. Willingness to practice a highly effective method of birth control with low user dependency from screening through one menstrual cycle after the last dose of study medication, which include:
 - i. Abstinence

- ii. Sex only with persons of the same sex
- iii. Monogamous relationship with vasectomized partner
- iv. Intrauterine device
- v. Combined estrogen and progestogen containing hormonal contraception associated with inhibition of ovulation (oral, intravaginal, transdermal)
- vi. Progestogen-only hormonal contraception associated with inhibition of ovulation (oral, injectable or implantable)

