5.3.3.12 Laboratory Evaluation

Hematology (including white blood cells (WBC), red blood cells, hemoglobin, hematocrit, mean corpuscular volume, mean corpuscular hemoglobin, mean corpuscular hemoglobin concentration, platelets, WBC differential (absolute and %), neutrophils, lymphocytes, monocytes, eosinophils, basophils); Liver Panel (including total and direct bilirubin, AST, ALT, total protein, albumin, GGT, lactate dehydrogenase, AP, INR); Serum Chemistry (including sodium, potassium, urea, creatinine, calcium, phosphate, glucose, creatine kinase) will be evaluated at each scheduled visit day during treatment period, as well as the scheduled days during Treatment follow-up period.

Urinalysis (including protein, bilirubin, urobilinogen, ketones, glucose, leukocyte esterase, red blood cells, pH, nitrites, specific gravity, microscopy) will only be evaluated in the same days during treatment period but not during the Treatment follow-up period.

The summary statistics (including number, mean, SD, median, Q1, Q3, minimum, and maximum) of all quantitative laboratory variables (laboratory values and changes from baseline) will be calculated for each dose during the treatment period and for each visit during the follow-up period, by treatment arm.

Laboratory data will be analyzed at pre-doses of Dose 1 to 6. For all parameters, the last available measurement after last dose and before the current dose will be the representative value to be summarized for each dose (ie: for dose 2, last value taken from "Date of dose 1 + 1 day until Date of dose 2").

For each visit during the follow-up period, the last of all measurements for the corresponding visit will be the representative value to be summarized.

The number (%) of patients with abnormal results (out of normal range) for each of the laboratory variables will be summarized at pre-dose of Doses 1 to 6 and in each visit during the follow-up period and treatment arm

22-Apr-2024

Shift tables for baseline versus each pre-dose for Doses 1 to 6 and follow-up visits will be presented for the hematology, urinallysis and chemistry laboratory parameters.

Data collected for Microscopy in Urinalysis (if clinically indicated or hemoglobin is detected on dipstick) will only be listed.

Data will be listed by patient.

Only available data will be used, and missing data will not be imputed.

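### The by-arm liver tables take the last value before each dose, so they pass over Days 8 and 36, give no rule for Day 169, and (ALT flares aside) do not count patients at the protocol's liver limits

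*SAP*

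**What the plan says.** SAP 5.3.3.12 sets the treatment-period time points for laboratory data at the pre-doses of Doses 1 to 6. Its rule, applied to every parameter, is that "the last available measurement after last dose and before the current dose will be the representative value to be summarized for each dose". The worked example for Dose 2 is the window "Date of dose 1 + 1 day until Date of dose 2", so a sample drawn on the dosing day falls inside it.

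Three by-arm displays use these points: descriptive statistics, shift tables, and a count at the limit of normal: "The number (%) of patients with abnormal results (out of normal range) for each of the laboratory variables will be summarized". Follow-up visits have their own rule (last measurement of the visit). In Appendix 1 the hematology and biochemistry tables are marked as running through Day 169.

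Protocol Table 1 (section 4.6) marks liver panels after the first dose on Days 8, 29, 36, 57, 85, 113, 141 and 169. Its footnote says that the safety labs "for Doses 1 and 2 will be obtained during the visits conducted 7±2 days after these doses of study medication", and "Safety labs after Dose 6 will be assessed at the Day 169 visit". Section 4.3 explains that the procedures guard "against hepatitis flares and liver function abnormalities that would preclude the scheduled administration of the next dose of study medication".

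SAP 4.3 and 5.3.3.8 plan a by-arm hepatitis flare table (14.3.6.1) at ALT >= 3 x ULN and > 100 U/L. It uses every ALT value in the treatment period, scheduled or repeated.

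**The concern.** The protocol takes panels about a week after Doses 1 and 2 to catch early liver abnormality, and it sets numerical limits at which dosing is interrupted or ended. The by-arm laboratory tables are instead built on the last value before the next injection, that is, on patients judged fit to be dosed again. A transient rise that settled before redosing, or a rise that ended dosing, can therefore be absent from them.

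The out-of-range count does not make up for this. It treats 1.1 x ULN and 4.9 x ULN alike, and it includes patients who entered under the steatosis allowance ("ALT and AST elevations up to 1.5 x ULN are allowed if evidence of hepatic steatosis"). The shift tables separate patients who were abnormal at baseline, but they use the same pre-dose points and specify no multiples of ULN.

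Safety is a secondary objective, and changes in AST, bilirubin and INR are named safety endpoints (protocol 3.4). SAP section 2 already reports no significant safety events. What is at stake is whether that statement rests on counts by arm.

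**Working it through.** The plan gives no figure to reproduce here. The check applies the SAP window rule to the Table 1 schedule and then sets the protocol's liver limits against the table index.

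**Which panels are tabulated.** The window for dose k runs from the day after dose k-1 to the day of dose k, and the last value is taken.

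| Dose | Window (days) | Scheduled panels | Value used |
|---|---|---|---|
| 2 | 2 to 29 | 8, 29 | 29 |
| 3 | 30 to 57 | 36, 57 | 57 |
| 4 | 58 to 85 | 85 | 85 |
| 5 | 86 to 113 | 113 | 113 |
| 6 | 114 to 141 | 141 | 141 |

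- Five of 8 panels are used. Days 8 and 36 are displaced: 2/8 = 25%, or 80 x 2 = 160 of 80 x 8 = 640 panels if all 80 patients complete.
- Day 169 is neither a pre-dose point nor a follow-up visit (protocol Table 2 starts at Day 232). The index implies that it will be shown, but 5.3.3.12 gives no rule for it. On the text of 5.3.3.12 alone, 3/8 = 37.5% (240 of 640) would be untabulated.
- If Day 29 is missed, Day 8 becomes the Dose 2 value. If Day 57 is missed, Day 36 becomes the Dose 3 value.

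**Whether a breach can appear at the next pre-dose point.** The protocol has two relevant texts: the dosing table in section 4.1, and section 6.4 (repeated in SAP 5.3.16), under which patients meeting a Stopping Rule end dosing permanently.

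- *ALT/AST 5 to < 10 x ULN, bilirubin and INR below their limits.* Dosing continues, so the peak may or may not be the last value.
- *ALT/AST >= 10 x ULN, bilirubin and INR below their limits.* Under section 4.1, "If ALT/AST fall to <5×ULN, restart dosing", so the last value before a restart is below the breach. Under section 6.4 there is no next dose and so no window.
- *ALT/AST >= 5 x ULN with raised bilirubin or INR.* Study medication is discontinued, so there is no later window. The Day 169/ET panel is drawn, but 5.3.3.12 has no rule for it.
- *Bilirubin >= 1.5 x ULN or INR >= 1.3 x ULN with ALT/AST < 5 x ULN.* Under section 4.1 the restart condition is worded with and/or, so a below-limit value on both is not guaranteed. Under section 6.4, a patient who also meets a Stopping Rule has no next dose.

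One exception applies throughout: a dosing-day sample whose result arrives after the injection can put a breaching value into the table.

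**What is counted at a limit.** Appendix 1 has the flare table for ALT. It has no by-arm count for AST at 5 or 10 x ULN, bilirubin at 1.5 x ULN, INR at 1.3 or 1.3 x ULN, or the combined criterion, and it does not grade ALT at 5 and 10 x ULN.

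**What a worst-value table would show.** Exact (Clopper-Pearson) 95% intervals with 40 per arm:

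- 0/40: upper limit 1 - 0.025^(1/40) = 8.8%, so 0 to 8.8%
- 1/40: 0.1 to 13.2%
- 2/40: 0.6 to 16.9%

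**The case against.** The strongest reply is that the main hepatic signal is already covered. The flare table counts by arm the one liver threshold that the protocol makes an endpoint, and it draws on Days 8, 36, 169 and repeat samples. If the ALT ULN exceeds 20 U/L (an assumption; 5 x 20 = 100), every patient with ALT >= 5 x ULN is also a flare patient, so the flare count is an upper bound for ALT at 5 and 10 x ULN. This stands. A reader might infer that no table counts any protocol liver limit, and the documents do not support that. The gap is AST, bilirubin, INR, the combined criterion and the grading of ALT.

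Second, breaches surface elsewhere. Listings are generally sorted by arm, and one covers eligibility for the next dose. Protocol 9.4 makes a confirmed abnormality that leads even to closer monitoring recordable as an adverse event. Early discontinuations are counted by arm with reasons, and adverse events leading to discontinuation have their own table. This also stands, but these routes depend partly on the investigator's judgment and on coded terms, and none gives a count at a stated limit.

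Third, the limits are operational rules applied during dosing, the laboratory endpoint is worded as changes, and neither document promises a table of breaches. That is fair: the plan breaks no promise. But it already chooses to count abnormal results, and it chooses a threshold and time points that suit the purpose poorly. For vital signs, SAP 5.3.3.11 does summarize Days 8, 36 and 169.

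**Conclusion.** The point holds as a gap in the by-arm summary tables. With panels drawn as scheduled, 2 of 8 post-first-dose panels are not tabulated, Day 169 lacks a rule, and a breach that ends dosing can be missing from the laboratory tables. Outside the ALT flare table, nothing counts patients at the protocol's liver limits.

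Two stronger readings should be resisted. Three of 8 panels lost would treat Day 169 as dropped, whereas the index shows that it was meant to be included. And nothing shows that liver data are lost or that a signal was missed: 160 of 640 counts panels, not abnormalities.

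The conclusion assumes that Days 29 and 57 are drawn as Table 1 marks them, and that the biochemistry tables include the liver panel, for which the index has no separate table. The weight is low. The study was terminated for lack of efficacy, the product will not be tested further, and no dosing or efficacy decision turns on this. It is a cheap improvement to the safety report.

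**What to change.** Add one descriptive by-arm table of the worst post-baseline value per patient, over all scheduled, repeat and weekly-monitoring samples from first dose to Day 169/ET. Count patients with:

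- ALT or AST >= 5 x ULN, and >= 10 x ULN
- total bilirubin >= 1.5 x ULN (direct bilirubin in Gilbert patients)
- INR >= 1.3 (Stopping Rule), and INR >= 1.3 x ULN (dosing table)
- ALT or AST >= 5 x ULN with bilirubin >= 1.5 x ULN (direct in Gilbert patients) or INR >= 1.3 x ULN in the same draw

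Give exact 95% confidence intervals and no test. State in SAP 5.3.3.12 which value represents Day 169/ET. Label the table as added after the interim analysis.

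The cost is one table from data already collected and one line of SAP text, with no added visits or samples. The drawbacks are that it is post hoc and descriptive, and that its intervals are wide.

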3.4. Safety Endpoints

- Incidence and severity of AEs, medically-attended AEs (MAEs), new-onset chronic illnesses (NCIs), and immune-mediated medical conditions (IMCs)
- Incidence and severity of local and systemic reactogenicity events
- Incidence and duration of hepatitis flares, defined as alanine aminotransferase (ALT) \geq 3 × upper limit of normal (ULN) and \geq 100 U/L
- Changes in ALT, aspartate aminotransferase (AST), alkaline phosphatase (AP), gamma glutamyl transferase (GGT), bilirubin total and direct, international normalized ratio (INR) and other laboratory parameters

Safety endpoints will be assessed separately for the 24-week Treatment Period and 52-week Follow-Up Period.

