8.3. Safety Assessments

8.3.1. Reactogenicity Assessments

Each patient will record local events, systemic events, and oral temperature in a diary daily for 7 days after each dose. Diaries will be distributed to patients at each dosing visit to record these events. Patients will also be provided thermometers for daily recording of temperatures and measuring devices for the recording the size of injection reactions. Events will be graded according to the FDA Guidance for Industry: Toxicity Grading Scale for Healthy Adult and Adolescent Volunteers Enrolled in Preventive Vaccine Clinical Trials [United States Food and Drug Administration 2007]. Unsolicited events reported by the patients outside of this 7-day reporting period will be recorded as AEs.

Microscopic hematuria will be assessed by urinalyses performed at the visits 7±2 days after Doses 1 and 2 of study medication, and after Doses 3, 4, 5, and 6 as per the Schedule of Events (Table 1).

Reactogenicity events will be categorized separately from AEs unless they are assessed as serious, in which case they will be reported as SAEs. A list of solicited reactogenicity events is provided in Appendix 1.

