8.3.3. Clinical Laboratory Tests

Blood samples for the safety laboratory tests listed in Table 3 will be collected according to the Schedule of Events (Section 4.6).

Table 3: Safety Laboratory Tests

Hematology

White blood cells (WBC) Platelets

Red blood cells WBC differential (absolute and %)

HemoglobinNeutrophilsHematocritLymphocytesMean corpuscular volumeMonocytesMean corpuscular hemoglobinEosinophilsMean corpuscular hemoglobin concentrationBasophils

Liver Panel

Total and direct bilirubin

Aspartate transaminase (AST)

Alanine aminotransferase (ALT)

Total protein

Albumin

Gamma-glutamyl transferase (GGT)

Lactate dehydrogenase

Alkaline phosphatase (AP)^a

International normalized ratio (INR)

Serum Chemistry

Sodium

Potassium

Urea

Creatinine

Calcium

Phosphate

Glucose

Creatine kinase^b

Urinalysis

Protein Red blood cells

Bilirubin pH Urobilinogen Nitrites

Ketones Specific gravity

Glucose Microscopy (if clinically indicated or Leukocyte esterase hemoglobin is detected on dipstick)

For the purpose of reactogenicity reporting, hematuria is defined as 3 or more red blood

cells per high powered field

Serology (at Screening only)					
HIV I and II	HDV antibodies				
HCV antibodies					
Drugs of abuse and alcohol screen (at Screening only) ^c					
Amphetamine/ecstasy	Opiates				
Ethanol	Benzodiazepines				
Cannabinoids	Methadone and/or metabolites				
Cocaine	Barbiturates				
Pregnancy test ^d					

Pregnancy test

Beta human chorionic gonadotropin

- a Alkaline phosphatase iso-enzymes (liver-specific and bile duct specific) will be measured if original alkaline phosphatase test result is above the upper limit of normal.
- b Creatine kinase MB or Troponin T will be measured where clinically indicated.
- c Sites may use locally available drugs of abuse panels and alcohol tests. The specific drugs may vary from the outlined list.
- d A serum pregnancy test will be performed in all women of childbearing potential at Screening. Urine pregnancy tests will be performed at other time points.

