Appendix 1 – Reactogenicity Events

The following reactogenicity events will be assessed by patients for 7 days after each dose of study medication and recorded in daily diaries.

Local (injection site) reactogenicity events

- Pain (pain on pressure)
- Pain (spontaneous pain without pressure)
- Erythema/Redness
- Swelling/hardening

Systemic reactogenicity events

- Headache
- Fatigue
- Myalgias (muscle aches)
- Nausea
- Vomiting
- Diarrhea
- Chills
- Fever
- Arthralgias (joint aches)

Note: Microscopic hematuria will be assessed by urinalyses performed at visits 7±2 days after each dose of study medication

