4.3 Safety Endpoints

- Incidence and severity of AEs, medically-attended AEs (MAEs), new-onset chronic illnesses (NCIs), and immune-mediated medical conditions (IMCs)
 - An MAE is an AE resulting in hospitalization, emergency room visit, or visit to or from medical personnel (other than routine health care visits).
 - An NCI is an AE that is new (i.e., not present at baseline) and typically chronic. Because of the significance of this designation for the patient's health and for evaluation of vaccine safety, NCIs are expected to be diagnoses, not symptoms, and the Investigator should record sufficient data in the source document to support the diagnosis.
 - An IMCs is any AE appearing in the list of AEs detailed in Appendix 2 of the protocol. Any AE
 assessed by the Investigator as immune-mediated but not appearing in the list will also be
 reported as an IMC.
- Incidence and severity of local and systemic reactogenicity events
 Reactogenicity local or systemic events, and oral temperature will be recorded by the patient in a diary daily for 7 days after each dose. Events will be graded according to the FDA Guidance for

Industry: Toxicity Grading Scale for Healthy Adult and Adolescent Volunteers Enrolled in Preventive Vaccine Clinical Trials [United States Food and Drug Administration 2007].

Reactogenicity events will be categorized separately from AEs unless they are assessed as serious, in which case they will be reported as SAEs. The solicited reactogenicity events are the following:

Local (injection site) reactogenicity events:

- Pain at injection site (without pressure)
- Redness
- Swelling or hardening
- Tenderness

Systemic reactogenicity events

- Fatigue
- Fever
- Chills
- Headache
- Muscle aches
- Joint aches
- Nausea
- Vomiting
- Diarrhoea

Unsolicited events reported by the patients outside of this 7-day reporting period will be recorded as AEs.

Incidence and duration of hepatitis flares;

Hepatitis flares are defined as alanine aminotransferase (ALT) \geq 3 × upper limit of normal (ULN) and > 100 U/L.

The incidence and duration of hepatitis flares will be estimated considering ALT values across all measurements taken (scheduled and repeated) during the treatment period, as follows:

- Incidence of hepatitis flares will be estimated with the number of episodes across measurements on the treatment period per patient.

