5.3.3.7 Reactogenicity Events

Each patient will record local events, systemic events, and oral temperature in a diary daily for 7 days after each dose. Incidence of reactogenicity events will be analyzed by treatment arm and dose number.

The number of patients with injection site reactogenicity events and each of the solicited events (Redness, Swelling or hardening, Pain at injection site (without pressure), tenderness) as well as with systemic reactogenicity events and each of the solicited events (fatigue, fever, chills, headache, muscle aches, joint aches, nausea, vomiting, diarrhoea) will be shown.

Also, number of events will be estimated for grouped injection site reactogenicity events (Redness, Swelling or hardening, Pain at injection site (without pressure), tenderness) and grouped systemic reactogenicity events (fatigue, fever, chills, headache, muscle aches, joint aches, nausea, vomiting, diarrhoea). Each event will be counted once by day of registration in the patient's diary card (i.e.: if the same event is registered for 3 different days in the diary card of a specific dose, 3 events will be counted for that dose).

Summaries will be performed for All events and also according to the grade Mild, Moderate and Severe. The size of reaction for Redness and Swelling (or hardening) will be assigned with the measurement in cm, being Mild from 2.5 to 5, Moderate larger than 5 to 10 and Severe larger than 10. Patients may have self reported events under 2.5 cm as an event, but following formal guidance these will not be reported as reactogenicity event in the statistical analysis.

A listing of all events recorded in the diary card will be included.

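### Microscopic hematuria has a protocol definition for reactogenicity reporting, but the SAP never tabulates it by arm and dose under that definition and does not declare the omission

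*SAP*

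**What the plan says.** **Protocol.** Section 3.4 names a safety endpoint: "Incidence and severity of local and systemic reactogenicity events". Section 8.3.1, on reactogenicity, says: "Microscopic hematuria will be assessed by urinalyses performed at the visits 7±2 days after Doses 1 and 2 of study medication". The same sentence extends the assessment to Doses 3 to 6 according to Table 1. Table 3 in section 8.3.3 supplies a case definition: "For the purpose of reactogenicity reporting, hematuria is defined as 3 or more red blood" cells per high-power field. Appendix 1, on reactogenicity events, bullets 4 local and 9 systemic diary events and adds beneath them: "Note: Microscopic hematuria will be assessed by urinalyses performed at visits 7±2 days after each dose of study medication".

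**SAP.** Section 4.3 opens its list with "The solicited reactogenicity events are the following" and names 4 local and 9 systemic events, without hematuria. Section 5.3.3.7 analyses reactogenicity by arm and dose number. For the systemic part it says that patients with "systemic reactogenicity events and each of the solicited events (fatigue, fever, chills, headache, muscle aches, joint aches, nausea, vomiting, diarrhoea) will be shown". Section 5.3.3.12 says of urine microscopy: "Data collected for Microscopy in Urinalysis (if clinically indicated or hemoglobin is detected on dipstick) will only be listed". The index in SAP Appendix 1 has one reactogenicity table, 14.3.5.1, marked for the final report. Section 5.3.17, on changes from the protocol's analyses, mentions only ECG parameters.

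**The concern.** A case definition written for reactogenicity reporting implies that something will be reported against it. Programmers who follow the SAP exactly will produce a reactogenicity table in which hematuria cannot appear, whatever its true frequency. The only output that holds the defining measurement, red cells per high-power field, is a by-patient listing.

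This leaves one component of a named safety endpoint without a count, a percentage or a comparison between arms. The SAP introduction already describes HepTcell as well tolerated, and no planned table supports that statement for hematuria as the protocol defines it.

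**Working it through.** No figure in the plan needs reproducing. The check is a cross-reading and a count of planned outputs.

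**1. Does the protocol place hematuria within reactogenicity?** Yes, in three places: the assessment section (8.3.1), the case definition (Table 3) and the note in Appendix 1. The note sits apart from the bullets. Those bullets are items that patients record in a diary, whereas hematuria needs a urine test.

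**2. Does the SAP carry it through?** No. The 4 + 9 = 13 events in SAP 4.3 and 5.3.3.7 exclude it, and the index has no hematuria table.

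**3. Count of outputs.** Incidence by arm and dose needs 6 doses × 2 arms = 12 cells. Cells planned under the 3-cell definition: 0.

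**4. How far do the general urinalysis summaries go?** SAP 5.3.3.12 includes urinary red blood cells among the urinalysis variables. It gives abnormal results by arm at the pre-dose point of Doses 1 to 6, with shift tables (Tables 14.3.4.3.1 to 14.3.4.3.4).
- Pre-dose 1 is baseline. Pre-dose 2 to 6 cover the intervals after Doses 1 to 5, at most 5 × 2 = 10 of the 12 cells.
- The criterion is being outside the normal range. Neither document says that this equals 3 cells per field.
- The value used is the last one before the next dose. Table 1 schedules safety laboratories at Days 8, 29, 36 and 57. When the Day 29 and Day 57 samples are taken, they displace Day 8 and Day 36, the scheduled 7±2-day samples.
- Dose 6 is followed by the Day 169 urinalysis. In the SAP text this is neither a pre-dose point nor a follow-up visit, and urinalysis is excluded from follow-up.

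**5. Sampling times side by side.**

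| Dose (day) | Appendix 1 note | 8.3.1, Table 1 and footnote o |
|---|---|---|
| 1 (Day 1), 2 (Day 29) | 7±2 days after dose | 7±2 days after dose (Days 8, 36) |
| 3 (57), 4 (85), 5 (113) | 7±2 days after dose | from 7 days after the dose until the next dose, 28 days on (85 − 57 = 28) |
| 6 (Day 141) | 7±2 days after dose | Day 169 visit, 169 − 141 = 28 days |

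The two columns agree for 2 of the 6 doses. SAP 5.3.3.9 and 5.3.3.11 record that visits on Days 64, 92, 120 and 148 were removed in a protocol revision. Those days fall 7 days after Doses 3 to 6 (57 + 7, 85 + 7, 113 + 7, 141 + 7). The documents do not say whether urine was collected at them.

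**The case against.** The strongest defence is that the SAP follows the protocol's own list. Section 8.3.1 refers to Appendix 1 for the solicited events, and Appendix 1 bullets 13 events with hematuria only as a note. SAP 4.3 has the same 4 local and 9 systemic events. This stands in part: the ambiguity begins in the protocol, and it would be wrong to say that the SAP deleted a bulleted solicited event. It does not account for the definition in Table 3, which is expressly for reactogenicity reporting, or for the silence of SAP 5.3.17.

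A reader might infer that hematuria is never reported at all. The documents do not support that. Microscopy is to be listed, and urinary red cell abnormalities are tabulated as in step 4. Protocol 9.4 also has clinically significant laboratory findings recorded as adverse events, which are summarized by arm. What is missing is the tabulation by arm and dose under the protocol definition.

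A reader might also infer that every Dose 3 to 6 sample comes about four weeks after the dose. Footnote o rules that out for Doses 3 to 5; only Dose 6 is tied to a visit at about 28 days.

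Nor is the defined event measured in every patient. Urinalysis is scheduled for all, but microscopy is done only when clinically indicated or when the dipstick shows hemoglobin. Any incidence table therefore needs a rule for patients without microscopy, and neither document gives one. Neither sets out a hematuria grade, and a laboratory result has no diary day, so it does not fit the severity and event-count layout of SAP 5.3.3.7. These points shape the fix but do not remove the gap.

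**Conclusion.** The point holds for tabulation under the protocol's definition: 0 of 12 arm-by-dose cells are planned, and the proxy reaches at most 10 under a different criterion and with different sample selection. The omission is undeclared.

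The documents give no hematuria rate, so the number of patients affected cannot be estimated. Nothing here shows that HepTcell causes hematuria or that the well-tolerated description is wrong; a reader might infer either, but the documents contain no supporting result. The primary efficacy analysis is untouched. This is a gap in safety reporting that is cheap to close and still relevant after termination, because Table 14.3.5.1 remains marked for the final report.

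The conclusion assumes that the Table 3 wording means what it says about reporting, and that the analysis follows the SAP text without unwritten additions.

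**What to change.** In SAP 5.3.3.7 and Table 14.3.5.1, add a separate laboratory-assessed row outside the diary-day counts and the mild/moderate/severe grading:
- Give n (%) of patients with at least 3 red cells per high-power field, by arm and dose.
- Use any urinalysis after that dose and up to the next one, including Days 8 and 36, with Day 169 for Dose 6.
- State as an assumption that a negative dipstick for hemoglobin without microscopy counts as absent.
- Show separately the patients not tested and those with a positive dipstick but no microscopy.
- Flag hematuria present at baseline.
- Report the actual days from dose to sample.
- Label the row as added after the interim analysis, since SAP version 2.0 already describes that analysis.

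If the sponsor prefers not to tabulate the event, SAP 5.3.17 should declare and justify the omission. In either case, protocol Appendix 1 must be reconciled with 8.3.1, Table 1 and footnote o on sampling time.

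The cost is one derivation, one table row and a wording correction, with no new patient contact. The drawback is that the row depends on an assumption for patients without microscopy, which is why the untested groups should be visible.
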